We will document intervention throughput, based on proportions and CIs of: i) cases in Group completing intervention (definition of completing = 70% of offered sessions); ii) cases accessing the pro bono solicitor. We will also report dropout reasons. To further understand the intervention delivery we will document contacts between facilitators and fathers (mode, frequency and reason). The intervention acceptability will further be assessed in the qualitative interviews with fathers and network of professionals for client experience of the programme.

To establish the feasibility of generalising the intervention, we will: i) document the intervention content and facilitators' training requirements; ii) identify processes for fidelity checks in a future trial; iii) investigate the perceived relevance of this intervention to professionals and facilitators and barriers to recruitment and retention, based on qualitative interviews with professionals; iv) scope other local authorities' provision and interest in intervention, and acceptability of a future RCT, based on scoping survey.

RQ4. Is a cost evaluation feasible and what are the recommended procedures to calculate it?

To explore the feasibility of conducting a cost evaluation in a future trial, we will: i) document "care as usual" for fathers taking part in the study, using administrative data; ii) scope comparable offers in other local authorities, via the stakeholders' survey; iii) scope costs of this intervention and comparable programmes, based on process data, professionals' interviews, and literature search.

RQ5. What is the most suitable design for a future large scale trial? Is randomisation feasible and acceptable?

To establish the feasibility and acceptability of a future trial, we will take into consideration the recruitment flow and results from the proportion tests above, particularly regarding referrals, recruitment and completion rates. Stakeholders' views regarding the relevance and barriers to generalising this intervention and a future evaluation in a RCT will also support recommendation for the design of a future trial.

A recommendation regarding the feasibility of a future trial will be reached based on overall study findings.

Project management

Personnel

Delivery team:

- [name], Parenting Practitioner, Southwark Family Early Help – Group intervention facilitator and support to evaluation.
- [name], Head of Family Early Help Service, London Borough of Southwark – institutional support to Group and study.

Evaluation team:

- [name], Child Attachment and Psychological Therapies Research Unit (ChAPTRe), Anna Freud – Principal Investigator.
- [name], ChAPTRe, Anna Freud – Co-Investigator.
- [name], ChAPTRe, Anna Freud – Co-Investigator.
- [name], ChAPTRe, Anna Freud – institutional support as director of ChAPTRe.
- [name], Anna Freud – Research Officer.
- Research assistant(s) TBC.

Timeline

Dates	Activity
May – June 2023	Submission of ethics application. Data governance set up. Study design agreed between partners.
June – August 2023	Set up advisory group. Data collection set up. Protocol finalised and published. Draft fathers interview schedule.
September 2023	Recruitment of first cohort. Baseline data collection of first cohort.
December 2023	Post-treatment data collection of first cohort.

January 2024	Recruitment of second cohort. Baseline data collection of second cohort.
February – March 2024	Draft professionals interview schedule. Recruit professionals for interviews. Design local authorities survey. Disseminate survey. Post-treatment data collection of second cohort.
April – July 2024	Recruitment of third cohort. Baseline data collection of third cohort. Run interviews with professionals. Continue collecting survey responses from local authorities. Post-treatment data collection of third cohort.
August – October 2024	Conclude data collection from all strands. Conduct literature search to inform future cost analysis. Qualitative and quantitative data analysis.
October 2024 – February 2025	Data analysis finalised. Final report and outputs.

Risks

	Column title
Possibility of not reaching recruitment targets	The risk of recruitment difficulties is low for this study as the intervention delivery partners are collaborating with the evaluation team to support recruitment. They have extensive experience recruiting fathers to take part in the Group and in a previous initial evaluation of the intervention. The Group will be delivered over three cohorts, allowing learning from the first to inform the subsequent approach to recruitment for the remaining cohorts. The delivery partner will advertise the Group amongst referrals early and with additional resources.

The research team will work with the delivery partners to support recruitment efforts (e.g., by creating a study leaflet). We will also use a flexible and compassionate approach to data collection to fit around the needs of the father and make the process accessible for them. **Low risk.**

Potential for high level of attrition and missing data

Previously, approximately 70% of fathers have completed the Group which suggests low rates of attrition can be expected. However, there is still a risk that they drop out of the Group and given the additional burden of taking part in the research, and the repetition of assessments for at least a second timepoint, there is a chance some may choose to withdraw from the study.

We have several measures in place to mitigate this risk. Our team has extensive experience of working with similar populations and achieving good levels of data completion, which will be facilitated further by the delivery partners being well integrated in the local authority. The study also aims to triangulate between a range of information sources, therefore a lower response rate among some participants should not have a major overall impact on the ability of the study to achieve its aims. In addition, participants will receive vouchers for their time each time they complete pre- and post-treatment assessments, and will be allowed to choose their preferred mode of data collection. Medium/Low risk.

Low engagement of local authority professionals

For the interviews with stakeholders at Southwark, we will opt for individual interviews to allow us to accommodate professionals' busy schedules. Offering both face to face and online modalities will also make these assessments more flexible and convenient to participants.

For the online survey to local authorities across the country, we will use a range of dissemination channels to maximise the numbers of professionals seeing the survey invitation. We will make the invitation attractive, and the actual survey will be kept short. Low risk.

Heavy reliance on a single practitioner for delivery of the Group intervention

Currently, the intervention is delivered by one practitioner (with support from additional facilitator(s)) and there is heavy reliance on him to recruit and facilitate the Group. This creates a risk for the sustainability of the programme if this practitioner became unavailable to deliver the sessions. The additional risk that this creates for a future scaling up of the intervention will be further investigated and mitigated in this study, by collecting more detailed information about the programme and the training requirements of additional practitioners for a future large-scale trial. Medium risk.

Lack of definition of the intervention

As a non-manualised and not previously published intervention, there is a risk that the programme will fail to be systematically replicated in other sites. To mitigate this risk, an intervention protocol is being developed by the delivery partner, and the research team will collect detailed information about the delivery of the sessions to inform fidelity checks in a future trial. **Low risk.**

Data collection from the child and partner

There is a possibility that partners and children decline taking part in the research, particularly if their relationship with the fathers are strained. To encourage partners' participation, partners will receive vouchers for their time

completing each set of questionnaires. In addition, limited outcome measures will be collected from the partner and child, to decrease participant burden. Again, a flexible and compassionate approach to data collection will be used to facilitate trust and accommodate the needs of participants. **Low risk.**

Research team becoming aware of elevated distress from parents or children

If parents or children are experiencing elevated distress (e.g., CORE-10 or SDQ symptoms in the clinical range), the research team will write a summary report to the referrer so that appropriate referrals or support can be put in place via the social worker.

Researchers will not be able to check the questionnaire responses immediately after completion. When participants' responses are checked and they indicate elevated distress, the researchers will also contact the participants via email or phone to remind them of the available sources of support, including how to access immediate support if needed. If relevant, safeguarding procedures will be followed. **Medium/Low risk.**

Safeguarding concerns

The Groups and the evaluation study will be conducted in the CSC setting, where participants will be referred by the social workers themselves. Therefore, participating fathers and their families will be known to the social workers and already be engaged with CSC when invited to the study. Social workers that will become involved in the study have existing training in safeguarding and risk management as part of their job. Moreover, the intervention is being delivered by practitioners who are experienced working with this population and are embedded in the local authority's Family Early Help Parenting Service. As part of this research project, we have established safeguarding procedures, including identified safeguarding leads in each of the partners – which will be followed whenever necessary. **Medium risk.**

Safeguarding risks to the research assistants when conducting in-person assessments will be mitigated by doing these assessments at the same venue as the Group or another appropriate venue of the local authority, within working hours; home visits will not be offered. **Low risk.**

Partners being unable to complete questionnaires with confidentiality and safety, and/or giving rise to safeguarding concerns

There is a risk that partners' responses to the questionnaires might not be honest, if they do not feel safe enough to do so. This risk is inherent to this type of study but mitigated by the option that is given to participants to choose their preferred method of completion.

Safeguarding concerns may still arise (e.g., from scores on IPV questionnaire), and if they do they will be dealt with by following the procedures agreed between the project partners which includes contacting the relevant safeguarding leads. In addition, partners' PIS contains contact details to domestic violence support services. **Medium risk.**

Compliance

Registration

This study will be registered with the Open Science Framework (OSF).

Ethics

Ethical approval will be obtained from UCL Ethical Review Board before recruitment commences in September 2023.

Consent

The study will be explained to all participants clearly and in an accessible way to them, using the information sheet as well as explaining verbally as much as it is required for each case. The research team will contact interested fathers to explain the study in detail and send them the participant information sheet (PIS). This contact will be attempted over the phone, which can be followed up by further telephone contacts, email, videocall, or in person at the first Group session. Participants will have the chance to ask questions at these various stages and in different modalities. The actual signing of the consent form will be done online using Microsoft Forms, though it may be done with the support of a research assistant in person.

Right to withdraw

Participants will be informed (in the PIS and ICF) of their right to withdraw from the study at any time without giving a reason and without the care they or their child(ren) receive, or their legal rights, being affected. If they wish for their personal data which has already been collected to be deleted, they must inform the research team of their decision to withdraw in the period of 2 weeks from completing their assessments. Partners or children's refusal or withdrawal of participation does not affect fathers' participation in the study or Group. Fathers' refusal or withdrawal of participation in the study does not affect their participation in the Group.

Protecting participants and researchers from harm

The research team are highly experienced in conducting research with vulnerable participants, including those involved with Children's Social Care (CSC), and have established ethically approved standard operating procedures for working with this population. For this specific study, any safeguarding concerns will be reported to and addressed with the support of the safeguarding leads at Anna Freud, Southwark CSC, and Foundations. This could include father, partner, or child's reports in the questionnaires, participants' communication to the researchers, or researchers' observations. In addition, if any participating parents or children are experiencing elevated distress (e.g., CORE-10 or SDQ symptoms in the clinical range), the research team will write a summary report to the referrer so that appropriate referrals or support can be put in place via the social worker.

The Group intervention and the evaluation study will be conducted in the CSC setting, where participants will be referred by the social workers themselves. Therefore, participating fathers and their families will be known to the social workers and already be engaged with CSC when invited to the study. Social workers that will become involved in the study have existing training in safeguarding and risk management as part of their job. Moreover, the intervention is being delivered by practitioners who are experienced working with this population and are employed by the local authority's Family Early Help. Accordingly, it is unlikely that any existing safeguarding

concerns will only become apparent as part of families' participation in the study. If they do, we will work closely with the safeguarding leads and the family's social worker to address them promptly and appropriately.

Participants will not be disadvantaged for taking part in the study. Parents who decline to participate in the study will still be able to take part in the Group intervention and will still receive care-as-usual from their local services. Some questionnaires ask about parents' wellbeing, parenting experiences, and violence, which can be sensitive, embarrassing and upsetting. Participants may choose to complete these without the presence of a researcher, or to skip items altogether. If in the presence of a researcher, the team will attempt to make participants at ease and interact with them in a compassionate and sensitive manner. All the members of the research team are highly experienced in working with vulnerable adults and research assistants will receive further training and support to work with this population in this study.

We will monitor adverse events about the father, their partner, or child(ren), such as new allegations or termination of parental rights. When appropriate (if it is likely that it may be related to the study), adverse events will also be reported to the Ethics committee.

There is a potential risk to the safety of research assistants who collect face to face data from participants. To mitigate that risk, assessments will be done at the same venue as the Group intervention sessions, or another appropriate venue of the local authority, in the presence of other research assistants as well as local staff and within working hours. Home visits will not be offered.

Confidentiality

All collected data will be kept confidential and stored in a pseudonymised or, when possible, anonymised, format throughout the study. Identifiable information (e.g. names and email addresses) will be kept separately from research data that will be used for analysis. For interview recordings, after transcription, data will be pseudonymised and the audio recordings deleted. All data will be kept secure in a local network drive and only accessible by the research team.

Data shared between the delivery partner and the research team will follow the procedures agreed in the DPIA and Data Sharing Agreement. This data will be shared in an anonymised or pseudonymised format.

During the focus groups, efforts will be made to ensure the confidentiality of those taking part. To do this, the importance of confidentiality will be explained at the start of the focus group. When reporting the research findings all data will be anonymised to prevent identification of participants.

All identifiable data will be deleted up to one year after the end of the study.

Data security

The study will take place in the United Kingdom and will comply with the UK General Data Protection Regulation (GDPR) and the Data Protection Act 2018. All systems and servers utilised by the web-based platforms used in this study are located within the EEA. A DPIA details all key data governance processes used in this study, and a data sharing agreement between all three organisations has been agreed based on it. Only members of the research team, who are all trained in information governance and DBS checked will have access to the data. Identifiable data, including signed consent forms, will be kept for up to 1 year after the end of the study.

Only non-identifiable data can be made available to other researchers in future.

Data Protection

Our overarching 'Research Data Protection Statement' is available here. The below is specifically relevant to the project to which this document applies. Any questions about this section can be submitted to [contact] with reference to the Data Protection Identifier (DPID) found in the table below.

Regulatory framework

Relevant legislation	UK Data Protection Act 2018 (DPA) UK General Data Protection Regulation (GDPR)
Data Protection Identifier (DPID)	3044
DPIA outcome/ risk level	High/Medium/Low
Type of data processing	Use (and share)
Categories of data subjects	List
Privacy notice	Link to PN

Personal data

Lawful basis	Performance of a task carried out in the public interest.
Justification for the lawful basis	Public Task as transferred by funder

Special category data

Lawful basis	Legitimate Interest
Justification for the lawful basis	For scientific and historical research or statistical purposes.

Roles

Data controller(s) Joint data controllers are Foundations and Anna Freud.

Data processor(s) Southwark Family Early Help.

Data sharing mode A secure portal and/or encrypted email

Archiving

Archiving Y

Archive used for this project Foundations/other

Linking to NPD and use of SRS

Name of the organisation(s) submitting data to the NPD team List organisations

Name of the organisation(s) accessing the matched NPD data List organisations

Retention and destruction

Expected date of report publication February 2025

Expected date of data destruction February 2035

If you are looking for further clarification regarding our data protection notification requirements they will either be found in the project specific Data Privacy Notice and/or our Privacy Policy on our website. If you have any further questions around either of these please submit them to [contact] with a reference to the Data Protection Identifier (DPID) found in the above table.

References

- Cabrera, N. J., Cook, G. A., McFadden, K. E., & Bradley, R. H. (2011). Father residence and father-child relationship quality: Peer relationships and externalizing behavioral problems. *Family Science, 2*(2), 109-119.
- Cabrera, N. J., Volling, B. L., & Barr, R. (2018). Fathers are parents, too! Widening the lens on parenting for children's development. *Child Development Perspectives, 12*(3), 152-157.
- Dagan, O., & Sagi-Schwartz, A. (2018). Early attachment network with mother and father: An unsettled issue. *Child Development Perspectives, 12*(2), 115-121.
- Flouri, E., & Buchanan, A. (2004). Early father's and mother's involvement and child's later educational outcomes. *British journal of educational psychology, 74*(2), 141-153
- Lamb, M.E. & Lewis, C. (2011). The role of parent-child relationships in child development. In *Developmental science* (pp. 477-526). Psychology Press.

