Group and of recruiting, retaining and collecting outcome data with the target population, to pave the way for a definitive trial of this intervention. The results of this study will be used to inform a larger definitive trial of this intervention in CSC. In the Table below we specify the research questions and how we aim to address them.

Generic questions	Specific questions	Indicators
1. Is it possible to recruit and retain participants to an evaluation of the Fathers Group and collect quality outcome data?	Q1. Is it feasible to recruit participants?	Recruitment pathways. Recruitment rate (to intervention and to study). Demographic characteristics of the sample. Scoping survey with other local authorities.
	Q2. Is it possible to retain participants throughout the evaluation?	Number of referrals, proportion consenting and completing the intervention ($\geq 70\%$ of sessions), proportion consenting to study and completing post-test.
	Q3. Is it possible to collect quality outcome data?	Participant retention rates at baseline, post-test and follow-up.
	Q4. Is a third assessment point at 3-month follow-up feasible?	Document drop-out reasons. Data completion rates. Qualitative findings from focus-group and 1:1 interviews with fathers to understand data collection experience.
	Q5. What strategies are effective for data collection?	Data collection approach – document comparative success of different strategies and modify accordingly.
2. Are the outcomes quantifiable?	Q1. Are the outcome measures acceptable and able to detect change?	Changes, specifically escalation and de-escalation, in CSC involvement, parental and caring responsibility, level of contact, and domestic violence reports.
	Q2. What is the distribution of the outcome measures?	Pre- and post-treatment outcome data using standardised measures: 1) father's reported child abuse potential (CAPI), 2) father's mental health and wellbeing (CORE-10, PSF-sf),
	Q3. What are the recommended outcome measures (and effect size estimates) and	3) father's parenting and family dynamics (SCORE-15, PSS, APQ, b-PSES),

procedures for a future trial?

4) children’s socio-emotional and behavioural difficulties (SDQ- parent, partner, and older-child report),

5) partner’s reported intimate partner violence occurrence (WAST) and SCORE-15;

6) stages of change (from URICA).

Qualitative focus groups and 1:1 interviews with fathers (to gather views regarding study processes and instruments)

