
Interview with professionals in the local authority
 
The interview schedule will be designed by the research team in collaboration with the delivery partner
	
A range of key stakeholders such as parenting practitioners, social work team managers (e.g., children in care team and child protection team) and other decision makers in the participating site will be invited to 1:1 interviews about their views of the programme, the local authority provision, and the constraints of a future large-scale trial of this kind (including views on randomisation). Potential participants will be identified with the support of the delivery partner.
 
Interviews will be conducted by the research team either online via Microsoft Teams or in person at the
	
Approx. 10
	
During 2024.

and the PPI advisory group.

delivery site. These interviews are expected to take approximately 30-60 minutes.

Interviews will be recorded using Microsoft Teams (if online) or a Dictaphone (if in person).

Survey to local authorities in the UK

An online survey using MS Forms will be disseminated to local authorities in the UK. We will use existing professional network newsletters, existing contacts, and online databases to disseminate this survey. The survey will assess offer and gaps in current service provision and interest in the Fathers Group, as well as views about a future large-scale trial of this kind.

Target min. 30 responses

During 2024.

It is expected the survey will take approximately 15 minutes to complete.

Administrative data

Administrative data including: children's social care involvement, parental responsibility and contact with children, and domestic abuse records, during the study period will be collected in two stages. The first is for fathers who take part in the Group, where social care notes will be accessed by the delivery partner and the information that is collected is pseudonymised before being shared with the research team.

48 + approx. 40

September 2023 – July 2024.

The second is for fathers who are referred to the Group but do not end up taking part, where group-level, fully anonymised data will be collected by the delivery partner and shared with the research team for analysis.

Process data

Numbers of participants contacted, consenting, attending, etc. will be recorded by the delivery and research teams.

Approx. 80

September 2023 – July 2024.

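### Reports the study sends to children's social care can enter the same notes that supply its escalation and domestic violence indicators, and nothing in the protocol marks their origin

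*Protocol*

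**What the plan says.** **Indicators.** In the Research questions table, generic question 2 (are the outcomes quantifiable), the first indicator is "Changes, specifically escalation and de-escalation, in CSC involvement, parental and caring responsibility, level of contact, and domestic violence reports".

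**Source.** The Administrative data row of the Data collection table states that social care involvement, "parental responsibility and contact with children, and domestic abuse records, during the study period will be collected in two stages". For fathers who take part, "social care notes will be accessed by the delivery partner and the information that is collected is pseudonymised before being shared with the research team". For referred fathers who do not take part (approx. 40), "group-level, fully anonymised data will be collected by the delivery partner and shared with the research team for analysis". The window is September 2023 to July 2024.

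**What the study sends out.** The Risks table says of safeguarding concerns, for instance from partners' intimate partner violence scores, that "they will be dealt with by following the procedures agreed between the project partners which includes contacting the relevant safeguarding leads". The Compliance section (protection from harm) names the leads: Anna Freud, Southwark CSC and Foundations. It adds that father, partner or child questionnaire answers can be the trigger. For clinical-range CORE-10 or SDQ scores, "the research team will write a summary report to the referrer so that appropriate referrals or support can be put in place", with action through the social worker.

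**Adverse events.** The same section states: "We will monitor adverse events about the father, their partner, or child(ren), such as new allegations or termination of parental rights". It gives no data source for them.

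**The concern.** The study's questionnaires can set off a report to the service whose notes are then read as an outcome. A partner who discloses violence at baseline, or a father or child with a clinical-range score, may gain a domestic abuse entry or a change in social care involvement because the study asked. In the extracted data that entry looks the same as one that arose on its own.

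This is detection bias, and it runs mainly towards apparent escalation. It matters because ability to detect change is one of the grounds for choosing the future trial's primary outcome. If study-prompted entries are mixed in, the team cannot judge whether these administrative indicators are usable. The referred non-participants are not described as completing questionnaires, so a side-by-side reading with them would be lopsided.

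**Working it through.** The protocol gives no figure to reproduce here. The check has two parts: the route and its timing, then a scale illustration.

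**Route**
1. Study questionnaires include CORE-10 and SDQ (fathers), SDQ (children aged 11–12), and WAST and SDQ (partners). Source: Data collection table.
2. Clinical-range CORE-10 or SDQ leads to a report to the referrer, who is usually a social care professional (Participants section). Safeguarding concerns go to leads that include Southwark CSC's.
3. The delivery partner extracts the indicators from Southwark's social care notes.
4. No section describes recording the origin of an entry, logging the reports sent, or separating study-prompted entries.

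**Timing**
- Baseline surveys are shared the week before the first session. The Timeline puts baseline collection in September 2023, January 2024 and April–July 2024.
- Post-treatment collection is in December 2023, February–March 2024 and April–July 2024.
- All six fall inside the September 2023 to July 2024 extraction window, so a prompted entry can land in the outcome period.

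**Scale (assumptions; the protocol gives no rates)**

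Let b be the proportion of fathers who would have an escalation or domestic violence record anyway, and s the proportion of the others who gain one only through a study report. Then observed proportion = b + (1 − b) × s, with n = 48 (3 cohorts × 16).

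| b | s | Observed | Approx. count of 48 |
|---|---|---|---|
| 10% | 0% | 10.0% | 5 |
| 10% | 5% | 0.10 + 0.90 × 0.05 = 14.5% | 7 |
| 10% | 10% | 0.10 + 0.90 × 0.10 = 19.0% | 9 |
| 10% | 20% | 0.10 + 0.90 × 0.20 = 28.0% | 13 |
| 20% | 0% | 20.0% | 10 |
| 20% | 5% | 0.20 + 0.80 × 0.05 = 24.0% | 12 |
| 20% | 10% | 0.20 + 0.80 × 0.10 = 28.0% | 13 |
| 20% | 20% | 0.20 + 0.80 × 0.20 = 36.0% | 17 |

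The Wilson 95% interval is 4.5 to 22.2% for 5/48 and 16.6 to 41.0% for 13/48.

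The excess over a group with the same b and no questionnaires is (1 − b) × s. For s from 5 to 20% that is 4.5 to 18 percentage points at b = 10%, and 4 to 16 at b = 20%. At s = 0 it is nil.

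The partner route alone gives a similar order. If all of the approx. 30 partners respond and 10 to 30% of them prompt a new entry (assumed), that is 3 to 9 fathers, or 3/48 = 6.3% to 9/48 = 18.8%.

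**The case against.** **The protocol expects this to be rare.** The Compliance section calls it unlikely that existing safeguarding concerns will surface only through the study, since families already have a social worker. That stands, and it could make the effect negligible. It does not cover distress reports, which follow by rule from a clinical-range score. The Risks table also allows that safeguarding concerns may still arise and rates that risk as medium.

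**The study is single-arm and descriptive.** The RQ2 analysis text does not name the administrative indicators, and pre/post differences are offered only as evidence of promise. A reader might infer that study-generated records will be counted as effects or harms of the Group. The documents do not support that. They do not say that a report becomes a domestic abuse entry or an escalation, and they plan no formal effect estimate on these records.

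**Adverse events.** A reader might infer that new allegations are also drawn from the notes. No source is given, so this is possible but not established. The protocol does consider relation to the study, though only for onward reporting to the ethics committee.

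**Added support between pre- and post-test.** A reader might infer that distress reports inflate CORE-10 and SDQ improvement. The text says only that support can be arranged, so extra support before post-test is assumed. Excluding reported participants would not settle the matter, because it selects on severity. Assume normal scores, no true change, a pre-post correlation of 0.6 and a cut-off at the mean. Those left then start 0.80 SD below the mean and regress to 0.6 × 0.80 = 0.48 SD below it, a spurious worsening of 0.32 SD.

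**It is a matter for the SAP or the extraction form.** The split in the tables could sit there. The origin of an entry could not: an analysis plan cannot recover a field that was never collected. The agreed safeguarding procedures and the data sharing agreement are not shown, so some record of reports may already exist.

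**Conclusion.** The point holds as a modest gap in data capture. Study-prompted reports can reach the notes used for the escalation and domestic violence indicators, the timing allows it, and the protocol states no means of telling such entries apart.

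The direction is mainly towards apparent escalation. The size cannot be known from the protocol: the illustrated 4 to 18 points rest wholly on assumed values of b and s, and on each counted report producing a new entry. If few reports are sent, the distortion is small, but without a log the study could not show that. The point supports an inexpensive improvement. It does not show that the study's conclusions would be wrong.

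**What to change.** 1. Keep a dated log, by study ID, of every safeguarding or distress report the research team sends.
2. Add one field to the administrative extraction: entry originated from a study report (yes, no, unknown).
3. Report the escalation and domestic violence indicators, and any new allegations monitored as adverse events, with and without study-originated entries.
4. Do not set these indicators beside the group-level data on referred non-participants without that split.
5. For CORE-10 and SDQ, state how many participants had a report sent before post-test, as a caveat to the pre/post change. Do not add an analysis that excludes them.

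The duty to report stays exactly as it is.

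The cost is one log, one extraction field and a second line in the tables, with no extra visits. The downside is smaller counts once study-originated entries are set aside, and some entries whose origin stays unknown.
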